**Table 3 Study plan detailing the procedures during the Treatment Period Year 2 through Year 3 or End of Study**

Visit Month (Year 2)	V15	V16	V17	V18	V19	V20 (M18)	V21	V22	V23	V24	V25	V26	V27 (M24)
Study Week (Year 2)	W56	W60	W64	W68	W72	W76	W80	W84	W88	W92	W96	W100	W104
Visit Month (Year 3)	V28	V29	V30	V31	V32	V33 (M30)	V34	V35	V36	V37	V38	V39	V40 (M36)
Study Week (Year 3)	W108	W112	W116	W120	W124	W128	W132	W136	W140	W144	W148	W152	W156 (EDV) a
Procedure/Visit Window	±7 D	±7 D	±7 D	±7 D	±7 D	±7 D	±7 D	±7 D	±7 D	±7 D	±7 D	±7 D	±7 D
Investigational product													
Investigational product administration n	X	X	X	X	X	X	X	X	X	X	X	X	X p

AE = adverse event; AESI = adverse event of special interest; AIS = adenocarcinoma in situ;

CIN = cervical intraepithelial neoplasia; CIS = carcinoma in situ;

D = day; DMARD = disease-modifying antirheumatic drug; dsDNA = double-stranded deoxyribonucleic acid; ECG = electrocardiogram; EDV = Early Discontinuation Visit;

LLOQ = lower limit of quantitation; M = month;

QFT-G = QuantiFERON®-TB

Gold; SAE = serious adverse event;

LE = systemic lupus erythematosus;

SOC = standard of care; TB = tuberculosis; V = Visit; W = week;

a Subjects who prematurely discontinue investigational product will have the Early Discontinuation Visit within 4 weeks after the last dose of investigational product.

b Females with intact cervix must have a Pap smear completed and without documented malignancy (eg. no signs of CIN grade III, CIS, or AIS) within 90 days before Day 1 or up until 30 days after randomization, ie, before dosing at V2. Pap smears should thereafter be performed yearly and all female subjects with an intact cervix should have a Pap smear performed within 3 months of the last IP dose, eg, at the end of study or at the early discontinuation visit. If the Pap smear is abnormal, but without malignancy, it should be repeated as per the subject's gynaecologist's recommendation. If the subject's gynaecologist has recommended a repeat Pap smear be performed at a specified interval, the Pap smear should be obtained as recommended and the report provided in the source document. Since access to a Pap smear may vary by country, the Sponsor recommends that local guidelines are used for obtaining routine follow-up Pap smears in females who have received immunomodulators or immunosuppressive treatment.

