c Interferon-gamma release assay (IGRA) using QFT-G In-Tube Test.

d If a subject has a newly positive QFT-G test at any time during the study or at Week 156, the subject will undergo a chest x-ray to rule out the presence of active TB or other clinically relevant findings. Posterior-anterior and lateral images are required.

- e If subject has a newly indeterminate QFT-G test, it must be repeated every 3 months for the first year and every 6 months thereafter unless it reverts to negative.
- f Investigators should apply local practices for safety monitoring, eg, by serum chemistry tests, in case SOC dose is changed, eg, increased, and/or new DMARD is added.
- g Urine pregnancy test in females of childbearing potential.
- h Only subjects with Hepatitis B core antibody positivity at enrolment of Studies D3461C00004 or D3461C00005. To remain eligible in the LTE study, subject Hepatitis B virus DNA levels must remain below the LLOQ as per the central laboratory.
- i [REDACTED]
- j [REDACTED]
- k [REDACTED]
- l [REDACTED]
- m Monthly tacrolimus trough levels in subjects receiving tacrolimus as standard of care SLE therapy. These subjects must maintain tacrolimus trough levels below the central laboratory upper limit of the therapeutic range based on monthly measurements.
- n Investigational product will be administered as an IV infusion via an infusion pump over a minimum of 30 minutes.
- o If the subject is unwilling to continue with any study visits, including EDV, or is willing to continue with only selected study assessments, at a minimum, these assessments should be completed.
- p No investigational product dosing occurs at Week 156 or EDV.

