Although the study will initially be completely double-blind (ie, blind for subjects, Investigators/site staff, and Sponsor/designated clinical research organisation [CRO]), at the conclusion of the Phase 3 Studies D3461C00004 or D3461C00005 treatment allocation for all subjects who were previously on active treatment will become known to the Sponsor staff and/or designated CRO. The blind will be maintained for the Investigator and investigational site staff, for select roles at the CRO, and for the subjects. Further details are described in a separate unblinding plan.

In general, the first dose of study drug in the LTE study (LTE Day 1/Visit 1/Week 0) should occur on the same day as the final study visit of the prior study (ie, Week 52); however, special circumstances may warrant a delay in subject randomisation of up to 30 days following the final visit of the prior study (ie, Week 52). Administration of study drug in the LTE study should not occur until all LTE Day 1/Visit 1/Week 0 evaluations are completed.

This LTE study includes:

- **Treatment Period:** A 156-week treatment period with investigational product administered Q4W from LTE Week 0 to LTE Week 152 for a total of 39 doses. During the treatment period, visits will be scheduled for each Q4W administration.
- **At LTE Week 156 (or after the last dose of investigational product)** subjects will continue in the study for another 8 weeks to complete a 12-week safety follow up after the last dose of investigational product (last dose of investigational product will be given at LTE Week 152).

The total study duration will be up to approximately 164 weeks (including a 12-week Follow up Period after administration of the final dose).

Once subjects have completed Studies D3461C00004 or D3461C00005 (through Week 52), signed the informed consent form, and met all study eligibility criteria, they may be included in the LTE study.

In the event a site has not obtained the required approval (e.g., regulatory authority, local ethics committee) by the time a subject is eligible to be randomised in the LTE study, the site may be allowed the time to obtain the approval(s).

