#### 3.1 Safety variables

The following primary safety data will be collected: AESIs and SAEs.

Other safety variables include adverse events (AEs), vital signs, physical examination, electrocardiograms (ECGs), flares as defined by a modification of the SELENA Flare Index using the SLEDAI-2K, haematology, clinical chemistry, and urinalysis.

Change from baseline to each post-treatment time point where scheduled assessments were made will be calculated for relevant measurements.

If not stated otherwise, on-treatment values are defined as values with an assessment date after the first administration of investigational product and on or before the date of last administration of investigational product + 28 days.

The restriction that “data from subjects discontinuing from the investigational product in studies D3461C00004 or D3461C00005, or who elect not to participate in the LTE, will be considered up to the adjusted analysis-defined visit window of Week 52 (ie, up to Day 378)” (see section 2.1.6) does only apply to visit-based analyses of safety variables.

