#### **4.2.1.4 ECGs**

The number and percentage of subjects with normal; abnormal, not clinically significant; and abnormal, clinically significant ECG results will be presented as a shift table from baseline to last on-treatment value.

Observed values and changes from baseline of ECG values will be summarised by parameter and visit using descriptive statistics. The summary statistics presented will be minimum, 1st quartile, median, 3rd quartile, maximum, mean, and SD.

For each ECG parameter with available criteria, the number and percentage of subjects with Potentially Clinically Significant post-baseline values and Potentially Clinically Significant changes from baseline, respectively, will be presented by parameter and criterion.

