#### **4.2.1.6 Laboratory variables**

Observed values and changes from baseline of laboratory data for haematology, clinical chemistry, and fasting lipid profile will be summarised by visit. The summary statistics presented will be minimum, 1st quartile, median, 3rd quartile, maximum, mean, and SD.

Shift plots (scatter plots) presenting baseline values versus minimum post-baseline values (neutrophils, lymphocytes, monocytes, and haemoglobin only) and maximum post-baseline values (creatinine, creatinine kinase, blood urea nitrogen, alanine aminotransferase, aspartate aminotransferase, bilirubin), respectively, will be provided. A diagonal reference line indicating no change and horizontal and vertical reference lines indicating the limits of the reference ranges will also be displayed on the shift plots.

If any laboratory variables show any unusual features (high or low values or a general shift in the data points) at specific visits, then shift plots of these data may also be produced. This will be discussed and agreed upon during the BDR meeting.

[figure not shown]
For each laboratory parameter with available criteria, the number and percentage of subjects with TELVC values will be summarised by visit. Additionally, the number and percentage of subjects with at least 1 TELVC value will be presented. Percentages will be based on subjects with a measurement at baseline and at least 1 subsequent measurement of the variable (at the respective visit).

[figure not shown]
The number and percentage of subjects with laboratory values below, within, or above the corresponding reference ranges [REDACTED] will be presented as shift tables from baseline to maximum and minimum on-treatment value, respectively.

[figure not shown]
Urinalysis will be summarised as shift tables from baseline to the last on-treatment value for each parameter. Furthermore, the number and percentage of subjects with treatment-emergent changes will be summarised by parameter. Percentages for the summary of treatment-emergent changes will be based on subjects with a measurement at baseline and at least 1 subsequent measurement of the variable.

[figure not shown]
In order to identify potential Hy's Law cases, a shift table of maximum on-treatment total bilirubin against maximum on-treatment ALT, and maximum on-treatment AST expressed as multiples of ULN will be presented.

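### The on-treatment cut-off (last dose + 28 days) falls exactly on the nominal LTE Week 156 visit with no allowance for the ±7-day windows, so compliant but slightly late end-of-treatment values drop out of four secondary safety displays

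*SAP*

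**What the plan says.** SAP Section 3.1 sets a default on-treatment period for safety values. It starts after the first infusion and includes assessments "on or before the date of last administration of investigational product + 28 days". The default holds unless stated otherwise, and nothing in the unredacted text states otherwise for ECG or laboratory data.

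Four displays rely on it:

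- SAP 4.2.1.4: the three-category ECG result "will be presented as a shift table from baseline to last on-treatment value".
- SAP 4.2.1.6: "Urinalysis will be summarised as shift tables from baseline to the last on-treatment value for each parameter".
- SAP 4.2.1.6: laboratory values against the reference ranges, as "shift tables from baseline to maximum and minimum on-treatment value, respectively".
- SAP 4.2.1.6: for potential Hy's Law cases, "a shift table of maximum on-treatment total bilirubin against maximum on-treatment ALT", and the same for AST.

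On timing, SAP 1.2 states that the "last dose of investigational product will be given at LTE Week 152". Protocol Table 3, footnote p, confirms: "No investigational product dosing occurs at Week 156 or EDV". Every visit in Table 3, including Weeks 152 and 156, has a window of ±7 days. A subject who stops early has the Early Discontinuation Visit "within 4 weeks after the last dose of investigational product" (Table 3, footnote a).

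**The concern.** For a completer, the cut-off and the scheduled end-of-treatment visit fall on the same day. A Week 156 visit held one day late, after a Week 152 dose on its nominal day, complies with the protocol, but its values are no longer on-treatment.

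The two last-value tables are meant to show the subject's state at the end of exposure. When Week 156 is excluded, an older value takes its place. Whether a completer contributes a value from the end of the third LTE year, or one 28 to 52 weeks older, then depends on a day or two of scheduling. In the maximum/minimum and bilirubin-versus-ALT/AST tables the subject stays in, but the final scheduled sample is not considered.

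Early discontinuers are largely spared, because their end-of-treatment visit is set inside the 28 days. The loss therefore falls on the subjects with the longest exposure, whom an extension study exists to describe.

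**Working it through.** **1. Does the cut-off coincide with the visit?** By the SAP's definition (SAP 4.1.2), LTE study day = 7 × week + 1.

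- Week 152 dose: 7 × 152 + 1 = Day 1065.
- Cut-off: 1065 + 28 = Day 1093.
- Week 156 visit: 7 × 156 + 1 = Day 1093.

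The coincidence is exact. (SAP Table 2 prints Day 1092 for Week 208, which is LTE Week 156. The SAP's own formula gives 1093, and the printed window of 1079 to 1106 fits 1093. This slip does not affect the on-treatment rule.)

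**2. What replaces an excluded Week 156 value?** From Week 56 on, Table 3 schedules:

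- ECG at Weeks 104 and 156 only, so the fallback is Week 104, which is 52 weeks earlier;
- chemistry, haematology and urinalysis at Weeks 76, 104, 128 and 156, so the fallback is Week 128, which is 28 weeks earlier.

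An unscheduled assessment in between could shorten the gap.

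**3. How many completers?** The documents give no figure and no distribution of actual visit dates. Let d152 and d156 be the deviations in whole days, from −7 to +7, from the nominal days. Week 156 is excluded when 28 + d156 − d152 > 28, that is, when d156 > d152. Results under assumed distributions (the normal ones rounded to whole days and confined to ±7):

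| Assumed timing | Week 152 dose on its day | Both visits vary independently |
|---|---|---|
| Uniform over ±7 days | 7/15 = 46.7% | 105/225 = 46.7% |
| Normal, SD 3 days | 43.3% | 45.2% |
| Normal, SD 2 days | 40.1% | 43.0% |
| Half exactly on the day, rest spread evenly | 25.0% | 36.6% |
| Normal, 1 day late on average, SD 3 days | 56.1% | 45.2% |

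The windows allow anything from 0% to 100%. If the two deviations are exchangeable, or Week 156 timing is symmetric around day 28, the share cannot exceed 50%. What raises it is Week 156 running late relative to the last dose: in the last row, equal lateness at both visits cancels.

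**4. Which extended limit closes the gap?** The largest in-window interval is 28 + 7 + 7 = 42 days.

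- Limit of +35 days: nothing is lost if the Week 152 dose was on its day. If both visits vary uniformly, exclusion needs d156 − d152 ≥ 8, which covers 7 + 6 + 5 + 4 + 3 + 2 + 1 = 28 of 225 pairs, or 12.4%.
- Limit of +42 days: 0% lost for in-window visits.
- Follow-up Visit 1 (protocol Table 4) is 56 ± 3 days after the final dose, so day 53 at the earliest. A 42-day limit stays clear of it.

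**The case against.** The strongest reply is that little is lost. A late Week 156 value remains in the by-visit summaries, because the SAP's Week 208 window runs to LTE Day 1106, or has no upper limit for variables not measured in follow-up. It remains in the Potentially Clinically Significant ECG counts, TELVC counts, shift plots and treatment-emergent urinalysis changes, all of which use post-baseline values. This is correct, so a reader who infers that affected completers lose their only Year 3 ECG goes too far: it drops out of one table. That table is, however, the only place in the unredacted text where the normal / abnormal / clinically significant category is tabulated.

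A reader might also infer that liver cases would be missed. The documents do not support this. SAP 3.1.6 flags subjects meeting the biochemical criteria at any point in the study, and SAP 4.2.1.6 lists them with all visits. Only the cross-table could miss a late value. In the maximum/minimum tables, Week 156 is one of 11 scheduled LTE chemistry samples (Weeks 0, 4, 8, 12, 24, 36, 52, 76, 104, 128 and 156). An entry changes only if that sample is the extreme and crosses a category. The percentages above are shares of completers with an excluded visit, not shares of changed entries.

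It can also be said that 28 days is a deliberate choice: one dosing interval, also used for AEs during treatment, flare person-time and exposure. That is a sound reason to leave those definitions alone. But an AE can start on any day, whereas an ECG exists only where a visit was scheduled, and here the visit is scheduled on the boundary.

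Finally, nothing shows a bias between treatment groups. This stands. The loss is confined to completers, and assumed annual dropout differs (20% on 300 mg, 30% on placebo), so equal loss is not guaranteed, but the documents give no direction.

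**Conclusion.** The mechanism follows from the documents without assumptions: the cut-off equals the nominal Week 156 day, both visits have ±7-day windows, and no allowance is visible. Its reach is four secondary displays. The two last-value shifts (ECG and urinalysis) suffer most, since a value 52 or 28 weeks older stands in for the final one. The laboratory maximum/minimum and bilirubin-versus-ALT/AST tables lose one sample per affected subject.

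The size is an assumption: roughly 25% to 47% of completers under symmetric timing, and above half if Week 156 tends to run late relative to the last dose. A reader might take about half as an expected value or a ceiling. It is neither, because the documents contain no visit-date distribution.

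The primary outcome is not touched: AESI and SAE rates count events up to last dose + 84 days. This is a cheap improvement to the end-of-exposure tables, not a threat to the trial's main conclusions.

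**What to change.** In SAP Section 3.1, for ECG, laboratory and urinalysis values only, adopt one of two rules:

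- on-treatment runs to last dose + 42 days (28 days plus the 7-day windows of both visits); or
- the Week 156 assessment counts as on-treatment only for subjects who received the Week 152 dose.

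Two simpler versions should be avoided. A +35-day limit leaves part of the gap open (step 4 of the working). Counting Week 156 for everyone is unbounded, because protocol 4.2.1 asks subjects who stop early to keep attending scheduled visits: someone who stopped at Week 20 and attended Week 156 would have a value 136 weeks after the last dose called on-treatment.

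Leave the AE windows unchanged. Apply the equivalent rule to feeder Week 52 for subjects dosed at feeder Week 48 who do not enter the LTE, after checking the feeder visit windows, which these documents do not give.

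The cost is one sentence in the SAP and one rule in the programs. The downside is that some values up to 14 days further from the last dose count as on-treatment, and that the ECG and laboratory period differs from the AE period, so table footnotes should state which applies.

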### 3.1.1 Adverse events

Adverse events experienced by the subjects will be collected throughout the entire studies and will be coded using the latest version of Medical Dictionary for Regulatory Activities (MedDRA).

Adverse event data will be categorised according to their onset date based on the last dose of administration in either the feeder studies or the LTE, whichever is later, as follows:

In general:

- AEs occurring during treatment:  
An AE during treatment is defined as an AE with a date of onset  $\geq$  day of first dose of investigational product and  $\leq$  date of last dose of investigational product + 28 days.
- AEs occurring during follow-up:  
An AE during follow-up is defined as an AE with a date of onset  $>$  date of last dose of investigational product + 28 days and  $\leq$  date of last dose of investigational product + 84 days.
- AEs occurring during treatment and follow-up:  
An AE during treatment and follow-up is defined as an AE with a date of onset  $\geq$  day of first dose of investigational product and  $\leq$  date of last dose of investigational product + 84 days

The following are exceptions:

- For subjects in the “Randomised Placebo” treatment group with a switch to anifrolumab 300 mg in the LTE study, AEs with a date of onset  $\geq$  day of first dose of investigational product in the LTE study will not be considered in the categories above, except for those with an onset on the day of first dose of investigational product in the LTE that are recorded in the Phase 3 feeder studies.
- For subjects in the “All Anifrolumab” treatment group who were randomised to placebo in the Phase 3 feeder studies, AEs with a date of onset  $<$  day of first dose of investigational product in the LTE study and those with an onset on the day of first dose of investigational product in the LTE that are recorded in the Phase 3 feeder studies will not be considered in the categories above.

In general, an AE during LTE is defined as an AE in the categories above with a date of onset  $\geq$  day of first dose of investigational product in the LTE study. AEs with onset on the day of first dose of investigational product in the LTE, but which were recorded in the Phase 3 feeder studies will not be considered as occurring during the LTE.

If an AE has a missing onset date, then unless the stop date of the AE indicates otherwise, it will be considered an AE in the categories above. Similarly, if an AE has a partial onset date, then unless the partial onset date or the stop date indicates otherwise, it will be considered an AE in the categories above. If the missing or partial start date does not allow an assignment of the event as during the Phase 3 feeder studies or the LTE study, the AE will be assigned to the study in which it was documented.

Adverse events of special interest are marked as such in the electronic Case Report Form (eCRF).

Major acute cardiovascular events (MACEs) will be determined according to the assessments of the Cardiovascular Event Adjudication Committee (CV-EAC).

An infusion-related reaction (as assessed by the investigator) is defined as an AE with a preferred term of “Infusion related reaction”.

An infection is defined as an AE within the MedDRA system organ class infections and infestations.

Opportunistic infections are those marked in the eCRF as assessed by the investigator as opportunistic and non-opportunistic infections are all infections not marked as opportunistic by the investigator.

Hypersensitivity is defined as adverse events with MedDRA preferred term (PT) = “Hypersensitivity” and Lower level term (LLT) = “Hypersensitivity reaction”.

Herpes zoster is further classified according to the information given on the Herpes zoster log as follows:

Category	Rash [Y/N]	Episode status of HZ Event [localized/ disseminated]	Specify Disseminated [cutaneous/ systemic]	Any organ involvement [Y/N]
Cutaneous (localised) herpes zoster	Y	Localized	[no rule]	N
Cutaneous disseminated herpes zoster	Y	Disseminated	Cutaneous	[no rule]
Visceral disseminated herpes zoster	[no rule]	Disseminated	Systemic	[no rule]

A COVID-19 related adverse event is defined as an AE with one of the following preferred terms: “Asymptomatic COVID-19”, “Congenital COVID-19”, “Coronavirus infection”, “Coronavirus pneumonia”, “Coronavirus test positive”, “COVID-19”, “COVID-19 pneumonia”, “Post-acute COVID-19 syndrome”, “SARS-CoV-2 antibody test positive”, “SARS-CoV-2 carrier”, “SARS-CoV-2 sepsis”, “SARS-CoV-2 test false negative”, “SARS-CoV-2 test positive”, “SARS-CoV-2 viraemia”, “Suspected COVID-19”, “Vaccine derived SARS-CoV-2 infection”.

Adverse events with missing intensity will be assumed to be severe. Events with missing relationship to study medication per the investigator will be assumed to be related. If no information about seriousness is available, the AE will be considered serious.

AEs and AEs leading to discontinuation of investigational product during treatment and follow-up will also be presented by time intervals of the first onset of the event. For this analysis, repeated events with the same preferred term will not be considered (i.e., if a subject has more than one event with the same preferred term, only the event with the earliest date of onset will be used). The following time intervals are defined for AEs during treatment and follow-up:

- Year 1:  
AEs with date of onset  $\geq$  date of first administration of investigational product and either  $<$  maximum of date of re-randomisation in LTE study and date of administration of IP in LTE study or from subjects who are not randomised into the LTE study (ie, all AEs documented in the Phase 3 feeder Studies D3461C00004 and D3461C00005 are considered AEs in Year 1). If the AE has an onset on the day of first dose of investigational product in the LTE and is recorded in the Phase 3 feeder studies, it will be considered during year 1.
- Year 2:  
AEs with date of onset  $\geq$  date of first administration of investigational product in LTE study and  $<$  date of first administration of investigational product in LTE study plus 364 days
- Year 3:  
AEs with date of onset  $\geq$  date of first administration of investigational product in LTE study plus 364 days and  $<$  date of first administration of investigational product in LTE study plus 728 days
- Year 4:  
AEs with date of onset  $\geq$  date of first administration of investigational product in LTE study plus 728 days and  $<$  date of first administration of investigational product in LTE study plus 1092 days
- After year 4:  
AEs with date of onset  $\geq$  date of first administration of investigational product in LTE study plus 1092 days

If an AE has a missing onset date, then unless the stop date of the AE indicates otherwise, it will be assigned to the “Year 1” time interval. Similarly, if an AE has a partial onset date, then unless the partial onset date or the stop date indicates otherwise, it will be assigned to the earliest time interval given the available date information. If the missing or partial start date does not allow an assignment of the event as during the Phase 3 feeder studies or the LTE study, the AE will be assigned to “Year 1” if documented in one of the Phase 3 feeder studies or to “Year 2” if documented in the LTE.

The event rate per 100 subject years is defined as the number of subjects with an event divided by the sum of exposure time in days in the respective time period for all subjects in the analysis set multiplied by 365.25 days/year multiplied by 100. The exposure in a time period for each subject will be calculated as end of period – start of period + 1 (e.g., as the earlier of either (date of last dose of investigational product + 84 days, or date of study discontinuation) - date of first dose of investigational product + 1 day for the summary of all AEs during treatment and follow-up; for AEs during treatment, the same definition will apply, with the exception of last dose of investigational product + 28 days will be used). For analyses based on LTE data only (e.g. AE rates for subjects switching from Placebo to 300 mg anifrolumab in the “All Anifrolumab” treatment group), the first administration of investigational product during the LTE will be considered as the start of the overall period. For analyses based on feeder study data only (e.g. AE rates for subjects switching from Placebo to 300 mg anifrolumab in the “All Randomised Placebo” treatment group), the end of the overall period will be defined as the first administration of investigational product in the LTE -1 day. If a subject discontinued during a period or had the last follow-up visit earlier than expected, the date of study discontinuation/end of study will be used as end of the respective period.

For AESIs, SAEs, and COVID-19 related analyses of AEs, additional analyses based on an alternative event rate per 100 subject years will be derived as the number of subjects with the respective AE divided by the sum of time at risk in days for all subjects in the analysis set multiplied by 36,525. The time at risk is defined as time (including start and end date) from start of period (e.g., date of first administration of investigational product for all AEs) to the date of first event, death, withdrawal of consent, or end of period, whatever comes first. The same considerations for analyses based on LTE/feeder phase 3 data only as defined above will apply for alternative event rates.

The time to first onset of a specific AESI category will be derived as date of first onset of any AE in the respective category – date of first administration of investigational product + 1. For time to event analyses based on LTE data only (e.g. for subjects switching from Placebo to 300 mg anifrolumab in the “All Anifrolumab” treatment group), the first administration of investigational product during the LTE will be used in the above. AEs with an onset date before the date of first administration of investigational product and AEs with an onset after 84 days after the date of last administration of investigational product will not be considered for the time to first onset of AESI. If a subject has no AESI in a specific category, the time to first onset will be censored at the date of last administration of investigational product + 84 days. For time to event analyses based on feeder study data only (e.g. for subjects switching from Placebo to 300 mg anifrolumab in the “All Randomised Placebo” treatment group), the

minimum of last administration of investigational product in the feeder study +84 days and first administration of investigational product in the LTE -1 day will be used in the above. If a subject discontinued the study or had the last follow-up visit earlier than expected, the date of study discontinuation/end of study will be used as the censoring date.

For time to event analyses and calculation of alternative event rates only, the following rules will be applied for imputing (partially) missing onset dates prior to analysis: If an AE has a (partially) missing onset date, it will be imputed with the earliest possible date on or after the day of first administration of investigational product given the available start and stop date information. If the available start or stop date information indicate that the AE started prior to first administration of investigational product, no imputation of the start date will be done.

For the by timepoint analysis of anaphylaxis, hypersensitivity, and infusion related reactions, an AE at a visit is defined as an AE with a date of onset  $\geq$  day of administration of investigational product at the respective visit and  $\leq$  date of administration of investigational product at the following visit (or  $\leq$  date of last dose of investigational product + 84 days for the last visit with investigational product). Analogous to assignment of AEs to time intervals, AEs with (partially) missing date will be assigned to the earliest possible visit giving the available start and stop date information, in the study (feeder phase 3 or LTE) they were recorded in.

